In the POC trial (Study 28980), an anabolic effect of sprifermin was demonstrated in subjects with Kellgren-Lawrence grades (KLG) of 2 or 3, confirming the appropriateness of Kellgren-Lawrence grades as a selection criterion.

However, in the POC trial, no minimal JSW was specified. The average JSW in the POC trial was approximately 3.5 mm and the minimum JSW was 0.2 mm. The requirement of JSW of at least 2.5 mm in the medial compartment in this trial will lead to the inclusion of patients with sufficient remaining interbone distance (i.e., a higher average JSW) that will thus permit demonstration of either progression (worsening) or improvement during the trial.

Malalignment will be limited to 5 degrees in order to limit confounding factors regarding biomechanical loading.

Women of childbearing potential will be allowed to participate in the trial, provided they adhere to the use of a highly effective method of contraception.

Dose and Dose Regimen

The aim of this trial is to optimize the dose and the dosing interval for sprifermin and to find a balance between effects on symptoms and structure.

OA is a chronic disease, and therefore treatment will most likely need to be repeated at regular intervals.

The use of repeated cycles of 3 once-weekly injections over 3 consecutive weeks is based on preclinical data generated in the dog meniscectomy model (see the sprifermin IB), which suggested that anabolic effects on cartilage tissue were more pronounced when a given dose of sprifermin was administered as three i.a. injections than when it was administered as a single injection.

In this trial, 2 dosage strengths of sprifermin (30 and 100 mcg) and 2 regimens (4 treatment cycles given at 6-month intervals and 2 treatment cycles given at a 12-month interval) will be used in this trial. Each regimen of sprifermin will be compared with placebo.

The 10 mcg dosage of sprifermin used in the POC trial will not be used in this trial: despite observation of some biological effect, there was limited effect on MRI or clinical outcomes with this dose. Furthermore, results from the POC trial suggested that an interval of 3 months between cycles may have been too short.

Trial Assessments

Evaluation of Structure by MRI and Choice of MRI as Primary Endpoint

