8.1 Sample Size

The sample size was determined from expected changes in the primary endpoint: the change from baseline in cartilage thickness in the total femorotibial joint as evaluated by MRI at 2 years.

[figure not shown]
This trial is set up to detect a potential dose relationship, based on the total dose of sprifermin received over the 2 years, in limiting the reduction of or increasing the cartilage thickness in the total femorotibial joint, assuming:

- A mean change from baseline at 2 years of
 - -0.03 mm in the placebo group (i.e., 0 mcg over 2 years)
 - -0.01 mm in the sprifermin 30 mcg once a year group (i.e., 180 mcg over 2 years)
 - +0.01 mm in the sprifermin 30 mcg twice a year group (i.e., 360 mcg over 2 years)
 - +0.01 mm in the sprifermin 100 mcg once a year group (i.e., 600 mcg over 2 years)
 - +0.03 mm in the sprifermin 100 mcg twice a year group (i.e., 1200 mcg over 2 years)
- A common SD (standard deviation) of 0.10 mm
- A type-one error, α , of the primary efficacy analysis set at 5% two-sided
- Normal distribution.

The above assumptions were based on available MRI data from the OAI (<http://oai.epi-ucsf.org/datarelease/>) and from the POC trial (28980; see [Figure 3](#)).

A minor deviation from linearity has been introduced in these hypotheses based on the expectation of similar changes for the sprifermin 30 mcg twice a year and sprifermin 100 mcg once a year groups. Indeed, according to the current knowledge of the biological mechanism of action of sprifermin, the treatment effect of the highest dose (100 mcg) given once a year could be similar to that of a lower dose (30 mcg) given twice a year. Moreover, the variability of the measure is large, and therefore a deviation from perfect linearity may be expected.

Figure 3 **Expected Mean Changes in Cartilage Thickness (mm) in Total Knee at 2 Years (SD = 0.10)**

OA: osteoarthritis; POC: proof of concept; SD: standard deviation

Calculations showed that:

- 55 evaluable subjects in each group (total 275 subjects) will ensure a power of 90% for detecting a linear dose relationship using a linear trend test,
- 76 evaluable subjects in each group (total 380 subjects) will ensure a power of 90% for detecting an overall treatment effect (meaning that at least one group differs from the other groups) as well.

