8.5.2 Analysis of Primary Endpoint

The primary endpoint is the change from baseline in cartilage thickness in the total femorotibial joint as evaluated by MRI at 2 years.

The cartilage thickness in the total femorotibial joint as evaluated by MRI will be tabulated per time point (visit) and treatment group, along with the absolute change from baseline and the percent change from baseline.

The treatment effect on the primary endpoint will be assessed through dose-ranging using a repeated measurement analysis of variance (ANOVA, using PROC MIXED in SAS) on absolute change from baseline, including the baseline value, the treatment group, the time, and the country as factors and including treatment by time as interaction.

The primary efficacy analysis will consist of testing the linear dose relationship and the overall treatment effect at 2 years. The significance level will be set at 5% two-sided for both tests.

For the linear dose relationship testing, the null and alternative hypotheses will be:

$$H_0: -2 \text{ Mean}_{(\text{Placebo})} - 1 \text{ Mean}_{(180 \text{ mcg})} + 0 \text{ Mean}_{(360 \text{ mcg})} + 1 \text{ Mean}_{(600 \text{ mcg})} + 2 \text{ Mean}_{(1200 \text{ mcg})} = 0$$

$$H_1: -2 \text{ Mean}_{(\text{Placebo})} - 1 \text{ Mean}_{(180 \text{ mcg})} + 0 \text{ Mean}_{(360 \text{ mcg})} + 1 \text{ Mean}_{(600 \text{ mcg})} + 2 \text{ Mean}_{(1200 \text{ mcg})} \neq 0$$

where the doses shown are the total doses of sprifermin to be administered over the DBPC treatment phase (see [Table 1](#)).

If the null hypothesis is rejected, the alternative hypothesis will be accepted and it will be concluded that there is a dose relationship versus placebo over time.

For the overall treatment effect testing, the null and alternative hypotheses will be:

$$H_0: \text{Mean}_{(\text{Placebo})} = \text{Mean}_{(180 \text{ mcg})} = \text{Mean}_{(360 \text{ mcg})} = \text{Mean}_{(600 \text{ mcg})} = \text{Mean}_{(1200 \text{ mcg})}$$

$$H_1: \text{Mean}(i) \neq \text{Mean}(j) \text{ for some } i \neq j \text{ and } i, j = \text{Placebo or } 180 \text{ mcg or } 360 \text{ mcg or } 600 \text{ mcg or } 1200 \text{ mcg.}$$

where the doses shown are the total doses of sprifermin to be administered over the DBPC treatment phase (see [Table 1](#)).

If the null hypothesis is rejected, the alternative hypothesis will be accepted and it will be concluded that there is at least one group that differs from the other groups.

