ANOVA models are used for several endpoints. For each endpoint all available time-points except LOCF (specified in table 3) should be included and summarized. The general model specification for model that include 4 post-baseline measurements (i.e. qMRI) in SAS will be:

```
proc mixed data=p3 method=reml;
  class grpn vs usubjid CNTRGR1N ;
 model &var. = grpn vs grpn*vs base CNTRGR1N / solution;
  repeated vs / subject=usubjid type=&type. r;
  lsmeans grpn / adjust=dunnett diff=control('1') cl;
  lsmeans grpn*vs / adjust=dunnett diff=control('1' 'Week 26') cl;
  lsmeans grpn*vs / adjust=dunnett diff=control('1' 'Week 52') cl;
  lsmeans grpn*vs / adjust=dunnett diff=control('1' 'Week 78') cl;
 lsmeans grpn*vs / adjust=dunnett diff=control('1' 'Week 104') cl;
  lsmeans grpn*vs / slice=vs;
  contrast 'Linear trend (overall)' grpn -2 -1 0 1 2;
  contrast 'Linear trend at Week 26' grpn -2 -1 0 1 2 grpn*vs -2 0 0 0 -1 0 0
0 0 0 0 0 1 0 0 0 2 0 0 0;
  contrast 'Linear trend at Week 52' grpn -2 -1 0 1 2 grpn*vs 0 -2 0 0 0 -1 0
0 0 0 0 0 0 1 0 0 0 2 0 0;
  contrast 'Linear trend at Week 78' grpn -2 -1 0 1 2 grpn*vs 0 0 -2 0 0 0 -1
0 0 0 0 0 0 0 1 0 0 0 2 0;
  contrast 'Linear trend at Week 104' grpn -2 -1 0 1 2 grpn*vs 0 0 0 -2 0 0 0
-1 0 0 0 0 0 0 0 1 0 0 0 2;
```

run;

12 Disposition of Subjects and Discontinuations

This section presents specifications for reporting subject disposition and treatment/trial discontinuations. Additionally, procedures for reporting protocol deviations are provided.

Subject disposition will be presented for all subjects and by treatment group in terms of:

- Total number of subjects screened (i.e. subjects who signed informed consent)
- Number and percentages of subjects discontinuing the trial prior to randomization divided by main reason for discontinuation (did not meet all eligibility criteria, withdrew consent, other), by country and site, and overall.
- Number and percentages of randomized subjects.
- Number and percentages of exposed subjects
- Number and percentages of randomized subjects who completed the DBPC treatment phase. For the 2-year analysis a completer is a subject with no date of study discontinuation before day 819.
- Number and percentages of randomized subjects who discontinued the trial after randomization, during DPBC i.e. before day 819, and during extended follow up phase (grouped by treatment) and main reason (AE, death, lost to follow-up, etc).

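### Rejecting the total-dose trend at Week 104 is to be read as a dose relationship, yet it can reject with no difference between 30 and 100 mcg, and the SAP omits the between-regimen comparisons that would show this

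*Protocol*

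**What the plan says.** Protocol 5.2 (Dose and Dose Regimen) states the purpose: "The aim of this trial is to optimize the dose and the dosing interval for sprifermin". Table 1 in Protocol 6.2 gives four active arms, each strength (30 or 100 mcg) being given either in all four cycles or in cycles 1 and 3 only, plus placebo.

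The primary analysis in Protocol 8.5.2 has two tests at 2 years, a linear trend over total dose and an overall comparison of the five means: "The significance level will be set at 5% two-sided for both tests". The SAP code (Section 11, ANOVA models) writes the trend as "contrast 'Linear trend at Week 104' grpn -2 -1 0 1 2", with matching interaction terms. Protocol 8.5.2 and SAP 16.1 attach the same conclusion to rejection of the trend hypothesis: "it will be concluded that there is a dose relationship versus placebo over time".

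The documents differ on what accompanies the trend test. The Protocol (synopsis and 8.5.2) plans pairwise comparisons of sprifermin with placebo and also among the sprifermin dose and regimen groups, each with a difference, 95% CI and p-value. SAP 16.1 confines them to sprifermin groups against placebo, and the code in SAP Section 11 requests only Dunnett comparisons with the control group. SAP Section 9, which lists changes from the protocol, does not mention this.

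**The concern.** The contrast includes placebo at one end, so a difference between placebo and any reasonably effective set of active arms pushes it upward, whether or not the active arms differ from one another. The written rule nevertheless turns rejection into a statement about dose. Total dose also merges two separate design choices, strength per injection and interval between active cycles, and the trial is meant to inform both.

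At stake is the regimen decision for Phase III. A drug for which 30 and 100 mcg do the same thing could be reported as showing a dose relationship. The SAP's model-based output would then contain no active-against-active estimate with a confidence interval to correct that impression.

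**Working it through.** **Inputs.** Planned mean changes (Protocol 8.1): placebo -0.03, 30 mcg once a year -0.01, 30 mcg twice a year +0.01, 100 mcg once a year +0.01, 100 mcg twice a year +0.03 mm. Common SD 0.10 mm, 5% two-sided, 55 evaluable per arm for the trend test and 76 for the overall test, 30% drop-out. Contrast coefficients from Protocol 8.5.2 and SAP Section 11. Powers use the planning model (independent groups, non-central t or F with 5(n - 1) df), not the repeated-measures model.

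**1. The plan's own figures reproduce.**
- Contrast: 0.06 + 0.01 + 0 + 0.01 + 0.06 = 0.14 mm.
- Trend, n = 55: SE = 0.10 × √(10/55) = 0.0426; 0.14/0.0426 = 3.28; power 90.5% (stated 90%).
- Overall test, n = 76: the squared deviations of the five means sum to 0.00208; λ = 76 × 0.00208/0.01 = 15.8; power 90.4% (stated 90%).
- 76/0.7 = 108.6, so 109 per arm and 545 in total, as stated.

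**2. The contrast when strength has no effect.** Write effects over placebo in the order placebo, 30 mcg × 2 cycles, 30 × 4, 100 × 2, 100 × 4.
- Only interval matters, (0, r, d, r, d): -r + 0 + r + 2d = 2d, whatever r is.
- All active arms alike, (0, d, d, d, d): -d + 0 + d + 2d = 2d.

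**3. How often it rejects in those cases.** At n = 76, SE = 0.10 × √(10/76) = 0.0363 mm.

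| Pattern | Contrast (mm) | Contrast/SE | Rejects |
|---|---|---|---|
| No strength effect, d = 0.03 | 0.06 | 1.65 | 38% |
| No strength effect, d = 0.04 | 0.08 | 2.21 | 59% |
| No strength effect, d = 0.05 | 0.10 | 2.76 | 79% |
| No strength effect, d = 0.06 | 0.12 | 3.31 | 91% |
| Planned means | 0.14 | 3.86 | 97% |

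The planned effects over placebo are 0.02, 0.04, 0.04 and 0.06 mm, so their average is 0.16/4 = 0.04 mm. Only the 100 mcg twice-a-year arm is assumed to reach 0.06 mm.

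**4. What would separate the factors.** With n = 76:
- Strength, (0 -1 -1 1 1)/2: planned value [(0.01 + 0.03) - (-0.01 + 0.01)]/2 = 0.02 mm.
- Interval, (0 -1 1 -1 1)/2: planned value [(0.01 + 0.03) - (-0.01 + 0.01)]/2 = 0.02 mm.
- SE of each: 0.10 × √(4/76)/2 = 0.0115 mm, against 0.10 × √(2/76) = 0.0162 mm for a single pairwise difference.
- 0.02/0.0115 = 1.74, so power is about 41% for each; 90% would need about 264 per arm.

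**5. Time since the last active injection (Protocol Table 1).** At Week 104 it is 104 - 80 = 24 weeks in the four-cycle arms and 104 - 54 = 50 weeks in the two-cycle arms. At the Week 78 MRI, before that day's injection, it is 78 - 54 = 24 weeks in every active arm, after three or two active cycles.

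**The case against.** The strongest reply is that the protocol never rests regimen choice on this one contrast. It plans the between-regimen comparisons, which include strength at fixed interval and interval at fixed strength. Protocol 8.5.5 adds modeling to support regimen selection, and 8.5.1 asks for caution with p-values and a global reading of the results. Protocol 8.1 says openly that the trend is on total dose and that "the treatment effect of the highest dose (100 mcg) given once a year could be similar to that of a lower dose" given twice a year. Sensitivity to a flat active response is common to trend tests that include placebo, and the per-arm estimates and the plot of all arms in SAP 16.1 would make a plateau visible.

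Most of this stands. A reader might infer that the trial cannot answer its dose and interval aim. The documents do not support that: it is true of this contrast, not of the protocol as a whole. The reply weakens at the SAP, where the between-regimen comparisons are missing from both text and code, and the modeling is left to a separate plan. Visible arm means are not an estimated difference with a CI, and none of these provisions alters the written conclusion.

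A reader might also infer from the unequal recency at Week 104 that the comparison of intervals there is invalid. That goes too far. Week 104 is 26 weeks after cycle 4 starts and 52 weeks after cycle 3 starts, so it closes a full dosing interval for both regimens. Waning between doses is part of what a regimen does, so this is a legitimate estimand. Week 78 answers a different question, and the SAP already has a trend contrast and placebo comparisons there.

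**Conclusion.** The concern holds in limited form. Rejection of the Week 104 contrast does not by itself show that strength or interval matters, and the SAP's model output contains no estimate that separates them.

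With no difference between 30 and 100 mcg, a dose relationship would be concluded 59% of the time at d = 0.04 mm and 91% at 0.06 mm. The higher figure should not be taken as the expected case, because it gives both four-cycle arms (or all active arms) an effect that the protocol assumes for one arm only. Nor is the contrast as large in these cases as under the plan: the two no-strength patterns match each other exactly (2d), but even at 0.06 mm they give 0.12 mm against the planned 0.14 mm. All of this assumes SD 0.10 mm, 76 evaluable per arm and the planning model.

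The primary test and its sample size are sound as calculated. Whether the between-regimen comparisons were dropped on purpose cannot be told from the documents.

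**What to change.** Keep the primary trend test, and make these changes:

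1. In Protocol 8.5.2 and SAP 16.1, reword the conclusion: rejection shows a treatment effect increasing along the ordered regimens including placebo, and does not by itself show that strength or interval matters.
2. Restore the protocol's comparisons between sprifermin regimens in SAP 16.1 and in the Section 11 code, or list and justify their removal in SAP Section 9.
3. Add ESTIMATE statements at Week 104 to the existing PROC MIXED model, with the CL option and a divisor of 2, for strength (0 -1 -1 1 1), interval (0 -1 1 -1 1) and optionally their interaction (0 1 -1 -1 1). CONTRAST statements would give tests only, and without the divisor the SE is 0.0229 rather than 0.0115 mm. The matching treatment-by-time coefficients are needed, as in the existing trend contrasts.
4. Optionally add the interval estimate at Week 78, labelled supportive.

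The cost is one reworded conclusion in each document and a few lines of code, with no new data. The drawbacks are a more modest dose claim and factor estimates with about 41% power for the planned 0.02 mm, so they should be reported as estimates with 95% CIs rather than as decisive tests.

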8.5.3 Analysis of Secondary Endpoints

Descriptive statistics for secondary efficacy endpoints will be presented by time point (visit) and treatment group.

The same ANOVA model used for the primary endpoint will be used to assess the treatment effect on continuous secondary endpoints such as MRI endpoints, WOMAC endpoints (total, pain, function, and stiffness scores), and X-ray endpoints at each time point and over time.

Logistic regression will be used to assess the treatment effect on the binary efficacy endpoints such as the OMERACT-OARSI responder rate. Point estimates for each pairwise comparison and corresponding 95% CIs and p-values will be provided.

8.5.4 Safety Analyses

Safety data will be summarized descriptively overall and by treatment group, using the Safety Analysis Set.

AEs will be coded using the latest available version of the Medical Dictionary for Regulatory Activities (MedDRA).

All local and systemic AEs will be reported overall, by severity, and by relationship to trial drug, and summaries will be prepared of events leading to discontinuation and events leading to death.

The incidence of protocol-defined AIRs and the incidence of surgical procedures occurring to the target knee during the trial will be tabulated separately.

Laboratory safety parameters and vital signs will be descriptively summarized as appropriate.

8.5.5 Analysis of Further Endpoints

The following domains will be described overall and by treatment group using summary statistics:

- Disposition of subjects and discontinuations
- Protocol deviations
- Demographics, medical history, and other baseline characteristics
- Past and concomitant medications and procedures, with particular attention to pain medications
- Treatment compliance and exposure, as assessed by the number of injections received

PK sample bioanalysis will be performed by Merck Serono NCD-DMPK; and PK data analyses, as well as investigation of the relationship between dosing (dose and regimen), cartilage structure, and clinical scores as a function of time will be performed by Merck Serono Exploratory Medicine.

Exploratory biomarker sample and data analyses will be performed under the responsibility of Merck Serono NCD – Biomarker Technologies. The sample analytes will be further specified in the Manual of Procedures (MOP), and data analysis will be described in an Exploratory Biomarkers Statistical Analysis Plan (SAP). Results will be reported separately in an Exploratory Biomarkers Report.

Analysis of Data from the Extended Follow-up Phase

Data reported during the extended follow-up phase will be presented mainly using descriptive statistics.

Exploratory Pharmacometric Modeling

A modeling analysis will be performed in order to evaluate the disease-modifying effect of sprifermin, i.e., improvement of cartilage structure and clinical symptoms (WOMAC).

In particular, the relationship between cartilage structure changes and improvement of clinical symptoms will be investigated, in order to support the selection of the optimal dose/dosing regimen for future trials.

In order to derive a better understanding of sprifermin effects, other potential influencing/confounding factors such as the placebo effect will be included in the model.

The development of the models implies a covariate analysis to explore the influence of various potential predictors of variability, e.g., demographics/anthropometrics, biomarkers (including PGt markers), and concomitant medications.

Finally, simulations will be performed to address various scenarios, to support decision making and planning of future studies.

Additional models focusing on other secondary/exploratory endpoints could be developed if deemed appropriate.

The details of modeling and simulation analyses will be described in a Modeling and Simulation Data Analysis Plan.

8.6 Interim Analysis

No interim analysis is planned.

An IDMC will be constituted and will perform periodic reviews to evaluate the safety of the subjects participating in the trial on an ongoing basis. Detailed description of the safety monitoring will be specified in a dedicated IDMC charter.

9 Ethical and Regulatory Aspects

9.1 Responsibilities of the Investigator

The Investigator is responsible for the conduct of the trial at his/her site. S/he will ensure that the trial is performed in accordance with the clinical trial protocol and with the ethical principles that have their origin in the Declaration of Helsinki, as well as with the ICH Note for Guidance on Good Clinical Practice (ICH Topic E6, 1996) and applicable regulatory requirements. In

particular, the Investigator must ensure that only subjects who have given their informed consent are included into the trial.

In 1998, the US Food and Drug Administration (FDA) introduced a regulation (21 CFR, Part 54) entitled “Financial Disclosure by Clinical Investigators”. For trials conducted in any country that could result in a product submission to the FDA for marketing approval and could contribute significantly to the demonstration of efficacy and safety of the IMP (named “covered trials” by the FDA), the Investigator and all sub-Investigators are obliged to disclose any financial interest which they, their spouses or their dependent children may have in the Sponsor or the Sponsor’s product under study. This information is required during the trial and for 12 months following completion of the trial.

9.2 Subject Information and Informed Consent

An unconditional prerequisite for a subject’s participation in the trial is his/her written informed consent. The subject’s written informed consent to participate in the trial must be given before any trial-related activities are carried out.

Adequate information must therefore be given to the subject by the Investigator before informed consent is obtained (a person designated by the Investigator may give the information, if permitted by local regulations). A subject information sheet in the local language and prepared in accordance with the Note for Guidance on Good Clinical Practice (ICH Topic E6, 1996) will be provided by the Sponsor for the purpose of obtaining informed consent. In addition to providing this written information to a potential subject, the Investigator or his/her designate will inform the subject verbally of all pertinent aspects of the trial. The language used in doing so must be chosen so that the information can be fully and readily understood by laypersons.

Depending on national regulations, a person other than the Investigator may inform the subject and sign the ICF, as above.

Where the information is provided by the Investigator, the ICF must be signed and personally dated by the subject and the Investigator.

The signed and dated declaration of informed consent will remain at the Investigator’s site, and must be safely archived by the Investigator so that the forms can be retrieved at any time for monitoring, auditing and inspection purposes. A copy of the signed and dated information and ICF should be provided to the subject prior to participation.

Whenever important new information becomes available that may be relevant to the subject’s consent, the written subject information sheet and any other written information provided to subjects will be revised by the Sponsor and be submitted again to the IEC/IRB for review and favorable opinion. The agreed, revised information will be provided to each subject in the trial for signing and dating. The Investigator will explain the changes to the previous version.

Pharmacogenetics Informed Consent

All subjects who are enrolled in the trial will be eligible to participate in the optional PGt analysis (except in countries where collection of PGt samples is not allowed). Participation is optional, and the subjects who choose to participate will need to sign a specific PGt ICF.

